11. MANAGEMENT AND REPORTING OF ADVERSE EVENTS/ADVERSE REACTIONS

11.1 Adverse Events

11.1.1 Definitions

An AE, in this study, is defined as any untoward medical occurrence in a subject administered Obizur. An AE can therefore be any unfavorable and unintended sign (e.g., an abnormal laboratory finding), symptom (e.g., rash, pain, discomfort, fever, dizziness, etc.), disease (e.g., peritonitis, bacteremia, etc.), or outcome of death.

11.1.1.1 Serious Adverse Event

A **serious** adverse event (SAE) is defined as an untoward medical occurrence that at any dose meets one or more of the following criteria:

- Outcome is fatal/results in death (including fetal death).
- Is life-threatening defined as an event in which the subject was, in the judgment of the investigator, at risk of death at the time of the event; it does not refer to an event that hypothetically might have caused death had it been more severe.
- Requires inpatient hospitalization or results in prolongation of an existing hospitalization inpatient hospitalization refers to any inpatient admission, regardless of length of stay.
- Results in persistent or significant disability/incapacity (i.e., a substantial disruption of a person's ability to conduct normal life functions).
- Is a congenital anomaly/birth defect
- Is a medically important event a medical event that may not be immediately life-threatening or result in death or require hospitalization but may jeopardize the subject or may require medical or surgical intervention to prevent one of the other outcomes listed in the definitions above. Examples of such events are:
 - ➤ Intensive treatment in an emergency room or at home for allergic bronchospasm, blood dyscrasias, or convulsions that do not result in hospitalization, or development of drug dependence or drug abuse
 - ➤ Reviewed and confirmed seroconversion for human immunodeficiency virus (HIV), hepatitis A virus (HAV), hepatitis B virus (HBV), hepatitis C virus (HCV), hepatitis E virus (HEV), or parvovirus B19 (B19V)
 - ➤ Thrombotic or embolic event (e.g., stroke, TIA, myocardial infarction, DVT, pulmonary embolism, etc.)

Uncomplicated pregnancies, following maternal or paternal exposure to product are not considered an (S)AE; however, any pregnancy complication or pregnancy termination by therapeutic, elective, or spontaneous abortion shall be considered an SAE.

11.1.1.2 Non-Serious Adverse Event

A **non-serious** AE is an AE that does not meet the criteria of an SAE.

11.1.1.3 Unexpected Adverse Events

An unexpected adverse event is an AE whose nature, severity, specificity, or outcome is not consistent with the term, representation, or description used in the Reference Safety Information (e.g., package insert). "Unexpected" also refers to AEs that are mentioned in the package insert as occurring with a class of drugs or as anticipated from the pharmacological properties of the drug, but are not specifically mentioned as occurring with the particular drug under investigation.

11.1.1.4 Preexisting Diseases

Preexisting diseases that are present before entry into the study are described in the medical history, and those that manifest with the same severity, frequency, or duration during the study, will not be recorded as SAEs. However, when there is an increase in the severity, duration, or frequency of a preexisting disease, and the event is considered an SAE, it must be described on the AE CRF.

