9. RESEARCH METHODS

9.1 Study Design

This study is a multi-center, uncontrolled, open-label, non-interventional postauthorization safety surveillance study to describe the use of Obizur in patients with AHA, and secondarily, where data are available, to describe the hemostatic effectiveness and immunogenicity of Obizur. Approximately 40 male and female patients ≥18 years of age with AHA in the United States will be enrolled over a 3.5 year period with follow-up from the date of treatment through 180 days; it is expected this prospective study will enroll up to two patients per month. Patients should be enrolled within five days of initiating Obizur to ensure unbiased prospective observation.

In addition, in an attempt to collect all safety and utilization data on patients treated with Obizur since Food and Drug Administration approval in October 2014, Baxalta will conduct a retrospective chart review on persons treated with Obizur prior to the prospective study start date. Baxalta expects there will be approximately 30 to 40 patients who were treated with Obizur prior to the study start date, on whom retrospective data will be collected.

Prospective data will be collected for each subject over a period of approximately 180 days from the time of Obizur treatment; in addition, data points that are retrospective in nature (such as comorbidities and prior medical treatment) will be obtained from the medical chart for the time period prior to Obizur treatment. A subject or a subject's legally authorized representative will provide signed informed consent according to local regulations, prior to data collection initiation. Signed informed consent should be obtained within five days of Obizur treatment for patients newly treated with Obizur.

Among patients in the retrospective cohort, for whom Obizur treatment occurred prior to initiation of the prospective study, signed informed consent will be obtained at the time the patient has a clinic visit. If the patient is deceased or lost to follow-up, only anonymized data will be collected from the medical chart and entered into the electronic data capture (EDC) system.

The choice of Obizur use is to be made *independent of and prior to* any decision by the subject or the subject's legally authorized representative to participate in this study. The treating physician will determine the treatment regimen, as well as frequency of laboratory and clinical assessments, according to routine clinical practice.

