9.2.4 Informed Consent and Enrollment

Any patient who provides informed consent (i.e., signs and dates the informed consent form and assent form, if applicable) is considered enrolled in the study. A legally authorized surrogate may also sign the informed consent. If the patient is deceased or lost to follow-up, only anonymized data will be collected from the medical chart and entered into the electronic data capture (EDC) system.

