9.3.8 Physical Examinations

At screening, if an abnormal condition is detected, the condition will be described on the medical history CRF. During follow-up, if a new abnormal or worsened abnormal pre-existing condition is detected, the condition will be described on the SAE CRF. If the abnormal value was not deemed an AE because it was due to an error, due to a pre-existing disease (described in Section 11.1.1.4), not clinically significant, a symptom of a new/worsened condition already recorded as an AE, or due to another issue that will be specified, the investigator will record the justification on the source record.

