11.1.2 Assessment of Adverse Events

Each SAE from time of Obizur treatment until study completion will be described on the SAE CRF using the medical diagnosis (preferred), or, if no diagnosis could be established at the time of reporting the SAE, a symptom or sign, in standard medical terminology in order to avoid the use of vague, ambiguous, or colloquial expressions (see definitions in Section 11.1). For the purpose of this study only SAEs will be collected. Reasons for collecting SAEs only include: patients enrolled in this study are often elderly with a multitude of comorbidities and high medication intake. Additionally, they are seriously diseased receiving treatment in intensive care units. Thus, making qualified assessments of non-serious AEs with respect to isolated medicinal products is next to impossible given the multitude of treatments administered concomitantly. Each AE will be evaluated by the investigator for:

- Seriousness as defined in Section 11.1.1.1
- Severity as defined in Section 11.1.2.1
- Causal relationship to Obizur exposure as defined in Section 11.1.2.2

For each SAE, the outcome (i.e., recovering/resolving, recovered/resolved, recovered/resolved with sequelae, not recovered/not resolved, fatal, unknown) and if applicable action taken (i.e., dose increased, dose not changed, dose reduced, drug interrupted, drug withdrawn, not applicable, or unknown) will also be recorded on the AE CRF. Recovering/resolving SAEs will be followed until resolution, or 180 days post Obizur administration, which is first. If the severity rating for an ongoing SAE changes before the event resolves, the original SAE report will be revised (i.e., the event will not be reported as separate SAE). During the course of any SAE, the highest severity rating will be reported.

Any pregnancy that occurs after administration of medicinal product Obizur will be reported on a Pregnancy Form and followed-up at one year post-delivery, if feasible.

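### The pre-existing disease rule (11.1.1.4) cuts off at study entry and the SAE rule (11.1.2) starts at Obizur treatment, so they conflict for persistent events that begin between infusion and consent

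*Protocol*

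**What the plan says.** **The exclusion rule.** Section 11.1.1.4 reads "Preexisting diseases that are present before entry into the study are described in the medical history", and adds that "those that manifest with the same severity, frequency, or duration during the study, will not be recorded as SAEs". There is an exception: "when there is an increase in the severity, duration, or frequency of a preexisting disease, and the event is considered an SAE", the event must be recorded.

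**What entry means.** Section 9.2.4: "Any patient who provides informed consent" "is considered enrolled in the study". Section 10.4 likewise requires a signed consent form before a patient enters the study.

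**When consent happens.** Section 9.1, on the prospective cohort: "Patients should be enrolled within five days of initiating Obizur to ensure unbiased prospective observation". Figure 1 (section 9.2.6) repeats the five-day allowance. For the retrospective cohort, section 9.1 places consent at a clinic visit and sets no limit. Patients who have died or been lost to follow-up contribute anonymized chart data instead.

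**The recording rule.** Section 11.1.2: "Each SAE from time of Obizur treatment until study completion will be described on the SAE CRF".

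**Screening.** Section 9.3.8: "At screening, if an abnormal condition is detected, the condition will be described on the medical history CRF". The same section sends conditions that are new or worse during follow-up to the SAE CRF. It cites 11.1.1.4 as one reason for not calling an abnormality an AE, with the justification kept in the source record.

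**The concern.** The primary objective (section 8.2) is the incidence of therapy-related SAEs, so the numerator depends on what reaches the SAE CRF. In an ordinary trial, consent comes before treatment, and a cut-off at study entry does no harm. Here the decision to use Obizur has to come before the decision to take part, so consent normally comes after exposure. A cut-off at consent then places some exposed time on the history side of the line.

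Take a deep vein thrombosis on day 2, consent on day 4, and no change afterwards. Section 11.1.1.1 lists DVT among its examples of serious events, and section 9.3.5 names thrombogenicity as a key safety concern. Under 11.1.2 it is an SAE to record. Under 11.1.1.4 read literally, it was there before entry and is not recorded as one.

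Any resulting error runs one way, downward. It would also differ between the two cohorts, which section 9.5 allows to be assessed together. Later analysis may not recover an event that was never put on the SAE CRF.

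**Working it through.** **1. The rules side by side, for an event with onset after first infusion and before consent**

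| Event | 11.1.1.4, read literally | 11.1.2 |
|---|---|---|
| Persists unchanged after consent | not recorded as an SAE | recorded |
| Worsens to SAE level after consent | recorded | recorded |
| Resolved before consent | does not continue unchanged into the study, so outside the exclusion | recorded |

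The conflict is confined to the first row. No text gives either section precedence.

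**2. Length of the interval**

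- Prospective: at most 5 of 180 follow-up days, 5/180 = 2.8%. This is a short stretch, but it is the one around dosing.
- Retrospective (30 to 40 patients expected): no stated limit. Section 9.1 dates approval to October 2014, and section 6 plans the first site for 30 September 2015. Counting back 180 days gives 3 April 2015. Anyone first treated before that date would have all 180 days behind them before any site opened.
- Patients included without consent: entry as 9.2.4 defines it never occurs, so 11.1.1.4 has no cut-off to apply.

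**3. Scale in the primary estimate**

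Inputs from section 9.5: n = 40, 5% with a related event, two-sided exact (Clopper-Pearson) 95% interval. For x events in n:

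lower = Beta(0.025; x, n − x + 1); upper = Beta(0.975; x + 1, n − x).

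The plan's own figure comes first. With x = 0.05 × 40 = 2, the limits are 0.61% and 16.92%. The protocol states 0.6% and 16.9%, so the figure reproduces.

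Then suppose events are filed as history:

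| Recorded | Proportion | Exact 95% CI |
|---|---|---|
| 2/40 (none lost) | 5.0% | 0.6% to 16.9% |
| 1/40 (one lost) | 2.5% | 0.1% to 13.2% |
| 0/40 (both lost) | 0% | 0% to 8.8% |

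The chance of recording no case at all in 40 patients, with true rate 5% and a fraction f of cases lost, is (1 − 0.05 × (1 − f))^40:

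- f = 0: 0.95^40 = 0.129
- f = 0.25: 0.9625^40 = 0.217
- f = 0.50: 0.975^40 = 0.363
- f = 0.75: 0.9875^40 = 0.605

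The values of f are assumptions. The protocol contains nothing from which f could be estimated.

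**The case against.** The best reply is that the protocol mostly puts time zero at treatment already. Section 11.1.2 is the operative recording rule and is explicit. Section 11.1.1 defines an AE by administration of Obizur. Section 9.1 runs follow-up from the date of treatment and takes comorbidities from the chart for the time before treatment. Table 1 collects SAEs at baseline. The retrospective cohort exists to capture all safety data since approval, which a consent cut-off would partly defeat. A site reading the whole document would probably let 11.1.2 govern.

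This stands against several stronger readings that a reader might infer:

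- *That SAEs between infusion and consent are lost.* They are captured wherever 11.1.2 is followed. What is shown is a contradiction.
- *That early hypersensitivity reactions are the main casualty.* An acute reaction that has resolved by consent does not continue unchanged, so the exclusion does not fit it. Persistent events such as thrombosis are the right example.
- *That 9.3.8 itself bars SAE recording.* It directs the condition to the medical history CRF but does not forbid an SAE entry as well. It contributes through its at-screening wording and its reference to 11.1.1.4.
- *That the loss can be put at, say, 10% to 40% of events, so that 5% is recorded as 4.5% to 3.0%.* The arithmetic, 0.05 × (1 − 0.10) and 0.05 × (1 − 0.40), is right. The share has no source in the protocol, and treating every event in the gap as lost presumes that every site ignores 11.1.2.

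The reply does not remove the conflict. Section 11.1.1.4 uses a different time zero from 11.1.2, and a site following it literally would be complying with the protocol.

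**Conclusion.** The contradiction is real and narrow. Sections 11.1.1.4 and 11.1.2 give opposite instructions for a condition that begins after the first Obizur infusion and before consent, and that persists without worsening. Where a site follows 11.1.1.4, the primary incidence is biased downward, with the larger exposure in the retrospective cohort because its gap is unlimited.

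The size of the bias cannot be stated: neither the share of events falling in the gap nor the way sites would resolve the conflict is in the protocol. The move from 5.0% to 2.5% for one lost event only shows how sensitive a numerator of about two is. It assumes the protocol's illustrative 5% rate in 40 patients. The stated confidence intervals and the sample size are unaffected.

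The conclusion rests on reading entry into the study as consent, which 9.2.4 and 10.4 support.

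**What to change.** - **Section 11.1.1.4:** replace the reference to study entry with the first Obizur infusion, so that pre-existing means present before that infusion. Add that any condition with onset or worsening on or after it that meets SAE criteria goes on the SAE CRF, whatever the consent date, in both cohorts.
- **Section 9.3.8:** keep the reference to screening, but limit the medical history route to conditions with onset before the first infusion. Conditions with later onset that meet SAE criteria go to the SAE CRF. The test should be date of onset and not date of detection: screening normally follows infusion, and a truly pre-existing condition first noted then still belongs in medical history.

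The cost is two wording changes and a line of CRF completion guidance. No change is needed to sample size, visits or analysis. The first-infusion cut-off also gives patients included without consent a usable boundary.

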11.1.2 Assessment of Adverse Events

Each SAE from time of Obizur treatment until study completion will be described on the SAE CRF using the medical diagnosis (preferred), or, if no diagnosis could be established at the time of reporting the SAE, a symptom or sign, in standard medical terminology in order to avoid the use of vague, ambiguous, or colloquial expressions (see definitions in Section 11.1). For the purpose of this study only SAEs will be collected. Reasons for collecting SAEs only include: patients enrolled in this study are often elderly with a multitude of comorbidities and high medication intake. Additionally, they are seriously diseased receiving treatment in intensive care units. Thus, making qualified assessments of non-serious AEs with respect to isolated medicinal products is next to impossible given the multitude of treatments administered concomitantly. Each AE will be evaluated by the investigator for:

- Seriousness as defined in Section 11.1.1.1
- Severity as defined in Section 11.1.2.1
- Causal relationship to Obizur exposure as defined in Section 11.1.2.2

For each SAE, the outcome (i.e., recovering/resolving, recovered/resolved, recovered/resolved with sequelae, not recovered/not resolved, fatal, unknown) and if applicable action taken (i.e., dose increased, dose not changed, dose reduced, drug interrupted, drug withdrawn, not applicable, or unknown) will also be recorded on the AE CRF. Recovering/resolving SAEs will be followed until resolution, or 180 days post Obizur administration, which is first. If the severity rating for an ongoing SAE changes before the event resolves, the original SAE report will be revised (i.e., the event will not be reported as separate SAE). During the course of any SAE, the highest severity rating will be reported.

Any pregnancy that occurs after administration of medicinal product Obizur will be reported on a Pregnancy Form and followed-up at one year post-delivery, if feasible.

11.1.2.1 Severity

The Investigator will assess the severity of each AE using his/her clinical expertise and judgment based on the most appropriate description below; only AEs considered serious will be reported in this study:

• Mild

- ➤ The AE is a transient discomfort and does not interfere in a significant manner with the subject's normal functioning level.
- ➤ The AE resolves spontaneously or may require minimal therapeutic intervention.

Moderate

- > The AE produces limited impairment of function and may require therapeutic intervention.
- ➤ The AE produces no sequela/saquelae.

Severe

- ➤ The AE results in a marked impairment of function and may lead to temporary inability to resume usual life pattern.
- ➤ The AE produces sequela/sequelae, which require (prolonged) therapeutic intervention.

11.1.2.2 Causality

Causality is a determination of whether there is a reasonable possibility that the medicinal product, Obizur, is etiologically related to/associated with the AE. Causality assessment includes, assessment of temporal relationships, dechallenge/rechallenge information, association (or lack of association) with underlying disease, presence (or absence) of a more likely cause, and physiological plausibility. For each SAE, the investigator will assess the causal relationship between the medicinal product Obizur and the SAE using his/her clinical expertise and judgment according to the following most appropriate algorithm for the circumstances of the SAE:

- Not related (both circumstances must be met)
 - ➤ Is due to underlying or concurrent illness, complications, concurrent treatments, or effects of concurrent drugs
 - ➤ Is not associated with the medicinal product Obizur (i.e., does not follow a reasonable temporal relationship to the administration of product or has a much more likely alternative etiology).
- Unlikely related (either one or both circumstances are met)
 - ➤ Has little or no temporal relationship to the medicinal product Obizur
 - > A more likely alternative etiology exists
- Possibly related (both circumstances must be met)
 - ➤ Follows a reasonable temporal relationship to the administration of medicinal product Obizur
 - ➤ An alternative etiology is equally or less likely compared to the potential relationship to the medicinal product Obizur
- Probably related (both circumstances must be met)
 - ➤ Follows a strong temporal relationship to the administration of medicinal product Obizur which may include but is not limited to the following:
 - Reappearance of a similar reaction upon re-administration (positive rechallenge)
 - o Positive results in a drug sensitivity test (skin test, etc.)
 - Toxic level of the product as evidenced by measurement of the product concentrations in the blood or other bodily fluid
 - Another etiology is unlikely or significantly less likely

11.2 Non-Medical Complaints

A non-medical complaint (NMC) is any alleged product deficiency that relates to identity, quality, durability, reliability, safety, effectiveness, or performance of the product but **does not result in an AE.** NMCs include but are not limited to the following:

- A failure of a product to exhibit its expected pharmacological activity and/or design function
- Missing components
- Damage to the product or unit carton
- A mislabeled product (potential counterfeiting/tampering)
- A bacteriological, chemical, or physical change or deterioration of the product that causes it to malfunction or to present a hazard or fail to meet label claims

Any NMCs of the product will be documented on an NMC form and reported to the MAH within one business day. If requested, defective product(s) will be returned to the MAH for inspection and analysis according to procedures.

12. PLANS FOR DISSEMINATING AND COMMUNICATING STUDY RESULTS

The investigator will comply with the publication policy as described in the Non-interventional Trial Agreement.

14. ANNEXES

14.1 List of Stand-Alone Documents

Documents listed in Annex 1 are maintained separately from the study protocol. They can be provided on request.

No.	Document Reference No.	Date	Title
1	Number	Not finalized	Study Organization
2	Number	Not finalized	Clinical Monitoring Plan
3	Number	Not finalized	Data Management Plan

